#### 1.2 Study Rationale

As belatacept comes into increasing clinical use, it is important to reach a better understanding of its immunologic mechanism of action. As the drug was engineered as a costimulation pathway inhibitor, we would hypothesize that its main effects would be on the activation of naïve T cells; however, an impact on pre-existing memory cells may also be seen. Both direct and indirect immunity play a role in allograft rejection after transplant, and it is important to differentiate between these two mechanisms as belatacept may affect each pathway differently: Direct recognition of alloantigen occurs when donor antigen presenting cells (APCs) present antigen to host T cell, as seen in early rejection, in contrast indirect recognition occurs when host APCs present either allo-antigen or viral antigen to host T cells.

It is known from Phase III trials that decreased formation of donor specific antibodies (DSA) are seen in patients treated de novo with belatacept compared with cyclosporine with both

standard and extended-criteria donors, [1,2] however, the mechanism behind this observation is unknown, and it is unclear whether this same affect might be anticipated in patients switched to belatacept one to three months post transplant. Finally, an increased frequency of post-transplant lymphoproliferative disorder in patients naïve for EBV with EBV positive donors (D+/R-) was also seen in these studies; this may reflect inhabitation of the development of antiviral immunity, but it is unclear how important the presence or lack of virus-specific memory T cells is in this response. Our laboratory is uniquely suited to perform a study of this nature given our experience and expertise in studies of immunity in transplant recipients as the designated investigative laboratory for the NIH-sponsored Clinical Trials in Organ Transplantation Study 2 (CTOT-2).

Figure 1: Model of belatacept action in alloimmunity and viral antigen recognition

Belatacept was designed as a co-stimulation inhibitor that is able to bind to CD80 molecules on the surface of antigen presenting cells, inhibiting the CD80-CD28 interaction that is required for T cell activation (figure 1).[3] Rodent models cannot be used for its study as the drug does not exhibit strong binding to murine CD80; preliminary efficacy and safety studies were therefore performed in primate models (see Investigator Brochure for additional details). No safety signal was seen in human Phase I trials, and Phase III studies have shown equivalence with or superiority to cyclosporine in prevention of death, graft loss, and chronic rejection, and an improved GFR as compared with cyclosporine treatment.[1,2] Overall safety profile was similar to cyclosporine, with the exception of PTLD which was seen with more frequency in the belatacept group, especially in patients naïve to EBV receiving transplants from an EBV seropositive donor.[4,5]

The calcineurin inhibitors, namely cyclosporine and tacrolimus, are widely used for immunosuppression in kidney transplantation. They have improved short term outcomes compared with earlier regimens such as azathioprine and steroids, but long term outcomes continue to be decreased by the nephrotoxicity related to long term calcineurin inhibitor use.[6]

#### 1.3 Rationale for Dosing

Based on the IM 103-116 study of conversion from CNI to belatacept for maintenance of immunosuppression in kidney transplant recipients, a similar dosing schedule will be used with belatacept 5mg/kg every two weeks for a total of 5 doses followed by monthly administration of belatacept at the 5mg/kg dose.

#### 1.4 Overall Risk/Benefit Assessment

Belatacept is an immunosuppressive drug with a novel mechanism of action compared with existing therapies that has been shown to be safe and efficacious in previous trials as described above. By enrolling patients exhibiting toxicity with standard CNI-based therapy, we will maximize the potential benefit to enrollees by allowing them the option to switch to a non-CNI based regimen with likely renal function improvement compared with standard therapy. The potential risk of increased acute rejection and PTLD will be meliorated by the close supervision that subjects will receive by the study team. Therefore, this study offers a favorable risk-benefit relationship to potential enrollees.

#### **2 STUDY OBJECTIVES**

#### 2.1 Primary Objectives

Primary Outcome Measures:

- Donor specific antibody testing at Month 6
- Cell surface cytokine secretion in response to donor cell antigen by direct and indirect stimulation at Month 6
- Cell surface cytokine secretion in response to CMV and EBV antigens by direct and indirect stimulation at Month 6
- Immunophenotyping to determine overall immune profile at Month 6
- Survival and rejection in patients switched to belatacept at 12 months post transplant as compared with patients treated with conventional therapy at our center.

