Test Product, Dose and Mode of Administration, Duration of Treatment: Study patients will receive intravenous belatacept at 5mg/kg every two weeks at day 1 and weeks 2, 4, 6, and 8, and then monthly at months 3, 4, and 5. At month 6 patients may elect to continue for an additional six month period of belatacept administration. Peripheral blood mononuclear cells (PBMCs) and sera for antibody testing will be collected at time of study entry and at 4, 8, 12, and 24 weeks after belatacept start, frozen and banked at our center, and analyzed in batch fashion for development of humoral and cell mediated immunity. Patients who elect to receive an additional 6 months of belatacept treatment will undergo additional immunologic analysis at 1 year after study entry.

Reference Therapy, Dose and Mode of Administration, Duration of Treatment: Immunologic evaluations performed on study patients will be compared with a matched group of 20

control patients receiving conventional immunosuppressive therapy and participating in an ongoing observational trial regarding immunologic mechanisms contributing to rejection in kidney transplant patients.

Criteria for Evaluation:

Primary Outcome Measures:

- Donor specific antibody testing at Month 6
- Cell surface cytokine secretion in response to donor cell antigen by direct and indirect stimulation at Month 6
- Cell surface cytokine secretion in response to CMV and EBV antigens by direct and indirect stimulation at Month 6
- Immunophenotyping to determine overall immune profile at Month 6
- Patient and functional graft survival in stable renal transplant recipients

Secondary Outcome Measures:

- Donor specific antibody testing at Months 1 and 3 (and month 12 if continuing in study)
- Cell surface cytokine secretion in response to donor cell antigen by direct and indirect stimulation at Months 1 and 3 (and month 12 if continuing in study)
- Cell surface cytokine secretion in response to CMV and EBV antigens by direct and indirect stimulation at Months 1 and 3 (and month 12 if continuing in study)

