10.5 Institutional Review Board (IRB)
10.6 Records Retention
11 GLOSSARY OF TERMS AND LIST OF ABBREVIATIONS
11.1 Glossary of Terms
11.2 List of Abbreviations
12 REFERENCES

#### **1 INTRODUCTION**

1.1 Research Hypothesis

**Primary Hypothesis:** 

Conversion from CNI-based therapy to belatacept will be safe and effective for prevention of rejection, with a significant impact on antibody and T cell-mediated immune response as compared with control patients as measured in peripheral blood at 6 months after belatacept conversion.

Outcomes to be tested:

- Belatacept-treated subjects will not have a greater incidence of SAEs as compared with control patients
- Belatacept-treated subjects will have similar rates of acute rejection as compared with control patients
- Belatacept-treated subjects will have a lower donor-specific antibody level at 6 months compared with control patients
- Belatacept-treated subjects will have a decrease in the frequency of alloantigen specific T cells over time as compared with control patients
- Belatacept-treated subjects will have a decrease in the frequency virus specific T cells over time as compared with control patients
- Belatacept-treated subjects will have a greater percentage of naïve and central memory T cells and a lower percentage of activated T cells as compared with control patients

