	Defined Cell Population	FITC	PE	PerCP	APC	Pac	PE-
						Blue	Cy7
1	Central/effector	CD57	CCR7	CD3	CD45RA	CD8	CD4
	memory, naïve T cells						
2	Activation, memory	CD45RA	CCR5	CD3	CD95	CD8	CD4
3	Activation, effectors	CD45RA	HLA-DR	CD3	CD38	CD8	CD4
4	NK cells	CD161	CD94	CD3	CD56	CD16	
5	B cells	CD19	CD27	CD20	CD38	CD3	
6	T regs	FoxP3	CD103	CD4	CD25	CD3	

In addition we will analyze rates of rejection and patient and graft survival at 6 and 12 months post transplant as compared with patients receiving conventional immunosuppression regimens at our center.

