#### 4.2 Analyses

#### Immunologic mechanisms

Primary endpoints will be patient immune analysis at 24 weeks (end of study) as compared with control patients at a comparable time point for DSA, frequency of alloantigen and viral antigen reactive cells, and frequency of the immunophenotypes described above, comparison to be performed by Mann Whitney U test. In addition, a comparison will be made between patients' baseline and week 24 levels. ANOVA repeated measurement analysis will be used to evaluate immune measurements taken over time as compared with control patients

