#### Efficacy and safety

As an additional primary analysis, subject and graft survival at 6 months will be determined within each group. GFR measured at baseline and months 1, 3, 6, and 12 months will be descriptively summarized. Cumulative rates of acute and chronic rejection, and chronic allograft nephropathy, will be summarized, as well as incidence of post-transplant diabetes.

All AEs and SAEs since transplantation will be summarized for the patients receiving belatacept. For the control patients, rates of rejection, PTLD, and death will be summarized.

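### The primary clinical outcome differs between sections in components, time point and comparison, and no section says where 12-month status comes from for patients who do not extend

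*Combined protocol and SAP*

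**What the plan says.** Five places define or analyze the clinical outcome.

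- Section 2.1, under primary outcome measures: "Survival and rejection in patients switched to belatacept at 12 months post transplant as compared with patients treated with conventional therapy at our center".
- Section 4.2, Efficacy and safety: "As an additional primary analysis, subject and graft survival at 6 months will be determined within each group". Rejection follows without the primary label: "Cumulative rates of acute and chronic rejection, and chronic allograft nephropathy, will be summarized". A later sentence adds a summary of rejection, PTLD and death for the controls.
- Section 3.1.3 plans to analyze "rates of rejection and patient and graft survival at 6 and 12 months post transplant" against conventionally treated patients at the center, and calls neither time point primary.
- The synopsis and section 3.3 use identical wording: "Patient and functional graft survival in stable renal transplant recipients".

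Rejection also belongs to the primary hypothesis. Section 1.1 lists among the outcomes to be tested: "Belatacept-treated subjects will have similar rates of acute rejection as compared with control patients".

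On follow-up, section 3.1.1 sets a 6-month study with an extension by patient preference. Section 4.2 treats week 24 as the end: "Primary endpoints will be patient immune analysis at 24 weeks (end of study"). Section 7.2.4 gives a week 48 visit only to patients who continue, and section 7.2.5 follows patients who stop the drug through the week 24 procedures. The legend to Figure 2 in section 7.1, by contrast, describes a 12-month study duration and calls the second six months of therapy optional. Section 4.2 also has a 12-month measurement: "GFR measured at baseline and months 1, 3, 6, and 12 months will be descriptively summarized".

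On early rejection, exclusion 9 in section 5.2 bars subjects with biopsy-proven acute rejection in the first three months after transplant. The matching criteria in section 3.1.3 are age, sex, donor type and DSA level.

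**The concern.** A primary clinical outcome needs its components, time point, origin and comparator fixed before anyone looks at the data. Here each of these either differs between sections or is left open. With 20 subjects, one event moves a rate by 5 percentage points (1/20), so whether rejection counts, and up to which date, can change the reported result visibly.

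Two further matters bear on the 12-month version. Scheduled visits do not reach 12 months after transplant for patients who decline the extension, and no other source is named. And because the rejection history rule applies to one group only, a rate counted from transplant compares a group selected to be free of early rejection with one that is not.

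**Working it through.** **1. The definitions side by side**

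| Section | Components | Time point | Origin | Comparison |
|---|---|---|---|---|
| Synopsis, 3.3 | patient and graft survival | none | none | none stated |
| 2.1 | survival, rejection | 12 months | transplant | conventional therapy at the center |
| 3.1.3 | rejection, patient and graft survival | 6 and 12 months, unranked | transplant | conventional regimens at the center |
| 4.2, labelled primary | patient and graft survival | 6 months | not given | each group on its own |
| 4.2, not labelled primary | rejection, both groups | none | not given | descriptive |

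Section 3.1.3 makes a transplant origin plausible for 4.2, but does not say so and does not say which time point leads. The missing origin matters. For a patient switched at 3 months, 6 months from transplant is 6 − 3 = 3 months after the switch, whereas 6 months from the switch is 3 + 6 = 9 months after transplant.

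**2. Where the visits fall**

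Inputs: entry at 0 to 3 months after transplant (synopsis, which allows a switch within the first three months; 7.2.1 for the screening window); last visit for non-extenders at week 24, and week 48 for extenders (7.2.4). One month is 30.4375 days. Visit time = entry + weeks × 7/30.4375, so 24 weeks = 5.52 months and 48 weeks = 11.04 months.

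| Entry (months) | Week 24 | 12 months minus week 24 | Week 48 |
|---|---|---|---|
| 0 | 5.52 | 6.48 | 11.04 |
| 1 | 6.52 | 5.48 | 12.04 |
| 2 | 7.52 | 4.48 | 13.04 |
| 3 | 8.52 | 3.48 | 14.04 |

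A non-extender's last scheduled visit is about 3.5 to 6.5 months before the time point in 2.1. For extenders, week 48 reaches 12 months if entry was at 12 − 11.04 = 0.96 months or later.

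**3. Is another source of 12-month status named?**

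Section 6.6 asks for follow-up over the whole study duration and mentions vital and allograft status, but the duration is itself in conflict (3.1.1 against the Figure 2 legend). Sections 6.2.6.5 and 7.3.3.1 leave biopsy to center practice, and 7.3.4 describes laboratory testing as part of ongoing care. These make center records a likely source. None states that 12-month survival and rejection will be taken from them for non-extenders.

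**4. Early rejection**

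A subject with biopsy-proven rejection before entry cannot enroll. A control with the same history can be matched, because the criteria do not mention it and the source study in 4.1 is open to all transplant recipients at the center. If rejection is counted from transplant, as 2.1 and 3.1.3 do, events before the matched subject's Day 1 can occur only in controls. The direction favors belatacept. The documents do not give the share of rejections that fall in that period, so no size follows.

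**The case against.** The strongest reply is that this is a 20-patient exploratory study with no power claim (3.4), that the clinical results in 4.2 are descriptive, and that the immune endpoints at week 24 carry the scientific weight. That limits the severity. It does not explain why one primary outcome has several definitions.

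A reader might infer that section 4.2 ignores rejection. It does not: rejection is summarized in both groups. What it lacks is a time point and the primary label.

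A reader might also infer that 12-month outcomes will be missing for non-extenders, or that the 12-month result will rest on extenders alone with a calculable loss of precision. The documents do not support this. No section plans an analysis restricted to scheduled visits, the visit list in 7.2.4 has no specific survival or rejection check for anyone, the number who will extend is not given, and the Figure 2 legend points to 12 months of study. The gap is an unstated source.

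It is equally tempting to put a figure on the early-rejection bias from the roughly 10% first-year rate in 7.3.6. That rate refers to a cyclosporine-based regimen and serves the early-termination rule, and its split over time is not given. Matching on DSA level might also limit some imbalance in antibody-mediated rejection. The direction stands, but the size is unknown.

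Finally, that the 20 matched patients are the clinical comparator is an inference. Sections 3.1.2 and 4.1 suggest it, while 2.1 and 3.1.3 say only patients at the center.

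**Conclusion.** The point holds as an internal conflict that should be fixed. The sections disagree on whether rejection is part of the primary clinical outcome, on 6 or 12 months, and on whether groups are compared; the origin in 4.2 and the identity of the comparator are left open. Follow-up length also conflicts, and the source of 12-month status for non-extenders is not stated. The interval of 3.5 to 6.5 months is time without a scheduled visit, assuming entry at 0 to 3 months; it is not a count of lost outcomes.

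The early-rejection asymmetry is a separate weakness in the same comparison. It arises only if events are counted from transplant and the controls are not screened for earlier rejection; its direction is toward belatacept and its size cannot be estimated from the documents. The week-24 immune endpoints do not depend on any of this.

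**What to change.** State one primary time point, one origin, one set of components (including whether rejection belongs) and one named comparator, identically in the synopsis, 2.1, 3.1.3, 3.3 and 4.2. Reconcile the study duration in 3.1.1 with the Figure 2 legend.

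If 12 months after transplant is kept, say that vital status, graft status and rejection at that date come from chart review for every dosed subject, whether or not the patient extends or stops the drug, and for the named controls.

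For the group comparison, count each control's events from the same time after transplant as the matched subject's Day 1, and use controls with no biopsy-proven rejection before that time. Report event proportions with confidence intervals.

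The cost is protocol wording, chart review of about 40 patients at one center (20 subjects and 20 controls, if the matched group is the comparator), a slightly narrower control pool, and confirmation that the observational study permits access to the controls' records, which the documents do not state. No additional visits are needed.

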#### 3.1.2 Overview

This is an open label, single center clinical trial. All subjects will have undergone kidney transplantation with induction immunosuppression and will be on maintenance therapy with a CNI (tacrolimus or cyclosporine) plus mycophenolate mofetil and corticosteroid maintenance therapy at the time of enrollment. 20 subjects with evidence of CNI toxicity (see definition below) in the first three months after transplant will be enrolled to switch to the belatacept regimen. These enrolled subjects will be compared with 20 matched patients from an ongoing observational study of kidney transplant patients at our center.

All subjects will also receive induction with basiliximab and a background maintenance immunosuppressive regimen of MMF and corticosteroids.

Study patients will receive intravenous belatacept at 5mg/kg every two weeks at day 1 and weeks 2, 4, 6, and 8, and then monthly at months 3, 4, and 5. At month 6 patients may elect to continue for an additional six-month period of belatacept administration

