#### 3.1.3 Primary Outcome Measures and Justification

Patients switched to the belatacept-based regimen will be compared to a group of matched patients on standard CNI-based immunosuppression regimen on the following primary outcome measures: (1) the donor specific antibody level, (2) the frequency of alloantigen and viral antigen reactive cells as measured by cell surface cytokine analysis, and (3) the frequency of immunophenotypes described below at Month 6. Matching will be performed based on age within 10 years, sex, deceased versus living transplant, and DSA level at time of enrollment.

The intent is to investigate differences in these measures as a means to determine the immunologic mechanism of action of belatacept. These endpoints were selected based on previous research showing that these measures are key determinants of immune function in transplant patients. In addition, baseline levels at time of enrollment of these endpoints will be compared with results from months 1, 3, and 6, as well as month 12 if patients elect to continue for an additional 6 months of belatacept therapy. Month 6 will be used as the primary measure of outcome for the immunologic assays, with months 1, 3 and 12 if applicable as the secondary measures.

To perform these mechanistic studies, blood from subjects will be collected at each study time point as described below and peripheral blood mononuclear cells (PBMCs) will be isolated and frozen for future analysis.

For analysis of response to alloantigen stimulation, PBMCs will be incubated with either intact donor cells or membrane preparations from donor cells to test either direct or indirect immunity, respectively. Following incubation, a cocktail of fluorescent-conjugated monoclonal antibodies will be added to detect relevant immunologic subclasses of cells as well as relevant surface cytokines and the percentage of each lymphocyte subset will be analyzed using flow cytometry according to previously published protocols developed at the UCLA Immunogenetics Center [7].

For analysis of response to viral antigens, PBMCs will be extracted and stored as described above using well-characterized CMV or EBV antigens for stimulation during the incubation period using a similar protocol adapted for detection of relevant antiviral immune lymphocytes.

Overall immune profile will also be analyzed by immunophenotyping using multiparameter flow cytometry using the panels described below:

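### The comparator for the primary survival and rejection outcome is not fixed: 2.1 and the end of 3.1.3 name conventionally treated patients at the center, while 1.1, 3.1.2 and 4.2 point to the 20 matched controls

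*Combined protocol and SAP*

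**What the plan says.** Two sets of passages bear on who the comparison patients are.

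- **Center patients.** Section 2.1 lists as a primary outcome "Survival and rejection in patients switched to belatacept at 12 months post transplant as compared with patients treated with conventional therapy at our center". Section 3.1.3 opens by saying that belatacept patients "will be compared to a group of matched patients on standard CNI-based immunosuppression regimen on the following primary outcome measures"; the three measures then numbered are all immunologic. It closes by adding rejection and patient and graft survival as a further analysis, "as compared with patients receiving conventional immunosuppression regimens at our center". The synopsis likewise ties the matched group of 20 to the immunologic evaluations.
- **Matched controls.** Section 3.1.2 compares enrolled subjects with "20 matched patients from an ongoing observational study of kidney transplant patients at our center" and does not limit this to any measure. Section 1.1 states the expectation that "Belatacept-treated subjects will have similar rates of acute rejection as compared with control patients". In 4.2, "subject and graft survival at 6 months will be determined within each group", and "For the control patients, rates of rejection, PTLD, and death will be summarized". The only control group that section 4 defines is the group of 20 in 4.1, drawn from the observational study by the matching criteria of 3.1.3.

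The synopsis and 3.3 list patient and graft survival as primary with no comparator.

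**The concern.** Survival and rejection form a listed primary outcome, and the plan does not settle what they are compared with. Section 3.1.3 uses different words for the immunologic comparator and for the clinical one, which suggests two different groups. Section 4.2 speaks as if there were only one. An analyst could take the center's conventionally treated patients, or the 20 matched controls, and call either per protocol. The study is open label (6.3), so that choice could be made with the belatacept results in view.

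The two groups need not be alike. Section 5.1 requires a first transplant. Section 5.2 excludes PRA of 30% or more at transplant, any prior solid organ transplant, and biopsy-proven acute rejection in the first three months. A center cohort taken literally from 2.1 carries none of these limits. It could include repeat recipients, sensitized recipients and early rejections that a belatacept subject cannot have had before entry. That would tend to raise the comparator's rejection rate and so favor belatacept.

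**Working it through.** **1. Passages side by side.**

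| Section | Outcome | Comparator as worded | Time point |
|---|---|---|---|
| 1.1 | Rejection (not survival) | Control patients | Not tied to rejection |
| 2.1 | Survival and rejection | Conventionally treated patients at the center | 12 months post transplant |
| 3.1.2 | Not limited | 20 matched patients | None |
| 3.1.3, start | Three immunologic measures | Matched patients | Month 6 |
| 3.1.3, end | Rejection and survival | Conventionally treated patients at the center | 6 and 12 months post transplant |
| 4.2 | Survival | Each group | 6 months |
| 4.2 | Rejection, death | Control patients | None for controls |

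No section says that the center patients are a separate cohort, and none says that they are the 20. That 1.1 and 4.2 mean the matched 20 is inferred from 3.1.2 and 4.1, but it is the natural reading.

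**2. The time points differ as well.** Entry is 0 to 3 months after transplant. If the 6 months in 4.2 run from entry, they fall 6 + 0 = 6 to 6 + 3 = 9 months after transplant. Twelve months post transplant falls 12 - 3 = 9 to 12 - 0 = 12 months after entry, beyond the 6-month study for anyone who does not extend.

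**3. How far the choice can move the rejection result.** The plan has no figure to reproduce, because 3.4 declines to estimate power. Inputs: 20 belatacept subjects (3.4); a 10% first-year rejection rate, the only event rate in the documents (7.3.6); and 20%, the two-fold level in the same section, so 0.20 × 20 = 4 events. The size of a center cohort is not given; I assume 100 to 1000.

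*Chance variation in 20 controls at a true 10%:* P(0) = 0.9^20 = 0.122; P(1) = 20 × 0.1 × 0.9^19 = 0.270; P(2) = 0.285. So P(0 or 1) = 0.39 and P(3 or more) = 1 - 0.122 - 0.270 - 0.285 = 0.32. With 4/20 on belatacept fixed, 0 or 1 control events show as +20 or +15 points, and 3 or more as +5 points or less. A large cohort would sit near +10.

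*Newcombe 95% interval for p1 - p2*, with Wilson limits (l, u) and d = p1 - p2:
lower = d - √[(p1 - l1)² + (u2 - p2)²]; upper = d + √[(u1 - p1)² + (p2 - l2)²].
Wilson limits: 4/20, 0.081 to 0.416; 2/20, 0.028 to 0.301; 10/100, 0.055 to 0.174.

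- 4/20 v 2/20: lower = 0.10 - √(0.119² + 0.201²) = -0.13; upper = 0.10 + √(0.216² + 0.072²) = +0.33.
- 4/20 v 10/100: lower = 0.10 - √(0.119² + 0.074²) = -0.04; upper = 0.10 + √(0.216² + 0.045²) = +0.32.
- 4/20 v 100/1000, same formula: -0.02 to +0.32.

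These figures give both comparators the same 10% rate. They show only sampling variation and precision. Any difference in case mix would come on top, and the documents give no figure for it.

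**4. Neither comparator is decisive.** Normal-approximation power for 20% v 10% at two-sided 0.05 is 14% with 20 v 20, and 28% to 35% with 20 v 100 to 1000. Reaching 80% would take 199 per group.

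**The case against.** The strongest reply is that there is one natural reading. The 20 controls are themselves conventionally treated patients at this center, so they fit the 2.1 wording; 3.1.2 compares subjects with them without restriction; and section 4 defines no other group. This stands in part. A reader might infer that the plan sets up two stated comparators, with 2.1 and 3.1.3 naming every conventionally treated patient at the center. The text does not support that: neither section says all, and no such cohort is defined. What remains is that 3.1.3 and the synopsis attach the matched group to the immunologic measures, and 3.1.3 then changes its wording for the clinical ones.

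Second, 4.2 plans only descriptive summaries of survival and rejection, in a study declared exploratory. This also stands: no hypothesis test is at risk. But 1.1 and 2.1 still state a comparison, and a descriptive contrast depends on its comparator too.

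Third, a reader might infer that 20 controls are needlessly few, since survival and rejection need no assay, and that several matches per subject are called for. The documents do not support this as a defect. With 10% in both groups, the Newcombe upper limit is √(0.201² + 0.072²) = +21.4 points for 2/20 v 2/20, and √(0.201² + 0.045²) = +20.6 for 2/20 v 10/100. The gain is nearly all in the lower limit (-21.4 to -10.4), while the interest is in excess rejection, where the 20 treated subjects are the constraint. The size of the observational pool is not given. DSA level is a matching criterion, and 4.1 mentions stored cells for these patients but not DSA results.

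Fourth, the matching criteria (age, sex, donor type, DSA level) do not name transplant history, PRA, early rejection or CNI toxicity either. This stands: naming the matched group settles which comparator is used but does not by itself make that group fully comparable.

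**Conclusion.** The point holds as an ambiguity in a primary outcome. The comparator for survival and rejection is not defined consistently, and an unmatched center contrast and a 20-control contrast could both be defended as planned. In the illustration, the observed rejection difference could move from about +10 points to +15 or +20, or to +5 or less, through the choice of comparator alone, and the lower confidence limit from -13 to between -4 and -2. This assumes 10% rejection in either comparator, 4/20 on belatacept and a center cohort of 100 to 1000. The likely direction of bias from an unmatched cohort, in favor of belatacept, follows from the eligibility criteria; its size cannot be derived from the documents. Neither choice would support a firm conclusion on rejection. The correction is worth making because it is cheap and concerns a primary outcome.

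**What to change.** In 2.1, 3.1.3 and 4.2, name the matched control group of 4.1 as the single comparator for survival and rejection, and add to 4.2 that the between-group difference will be reported with a 95% CI. If a center-wide comparison is wanted, label it as supportive, give its calendar period and start of follow-up, and restrict it to patients who meet the same transplant-history, PRA and early-rejection criteria as the belatacept subjects. State whether the 20 matched controls must meet those criteria too.

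Reconcile the time points in the same sentences (12 months post transplant in 2.1; 6 and 12 months post transplant in 3.1.3; 6 months in 4.2), and say whether time runs from transplant or from entry.

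Further matched controls with clinical data only are optional, subject to the size of the pool and the availability of DSA results. They would not materially tighten the upper limit on excess rejection.

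The cost is wording in three sections and a slightly less flexible report. No enrolment or assay is added.
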